#### **6.6 Surgery During Trial Period**

Patients should not schedule any elective surgeries during their participation in the trial, through 7 days after the last administration of AM0010 or nivolumab. If a patient undergoes any unexpected surgery during the course of the trial, that patient must discontinue trial treatment immediately, and Lilly or its designee should be notified as soon as possible.

## **7.0 TRIAL ASSESSMENTS AND PROCEDURES**

### **7.1 General Trial Procedures**

Both trial Arm 1 and Arm 2 will follow the same schedule of assessment, unless otherwise noted.

A signed and dated IRB-approved ICF must be obtained before performing any trial-specific screening procedures that is not part of standard medical practice. All screening tests and assessments must be performed within 21 days of trial day 1, unless noted below.

During the trial, every effort should be made to keep the schedule of assessments on time for each patient ([Appendix A](#)). All visits should be performed on the visit specified  $\pm 1$  day, unless otherwise noted.

Patients will continue to receive trial treatment until progressive disease, unacceptable toxicity, require subsequent anticancer therapy, withdraw consent, or their physician feels it is no longer in their best interest to continue on treatment.

Tumor assessment will be performed for all randomized patients every 8 weeks ( $\pm 7$  days) during the study treatment and during the first year from discontinuation of the study treatment, every 12 weeks ( $\pm 7$  days) during the second year, and every 16 weeks ( $\pm 7$  days) thereafter. Tumor assessment will be repeated until disease progression, death, or receipt of new anti-cancer therapy, or until study completion, whichever is first, whether or not study treatment was administered.

Scans will include CAPs and head, and will be sent to the central imaging vendor for archiving. If clinical progression is suspected, all relevant clinical documentation is to be submitted to the central imaging vendor for archiving.

Tumor assessment of all sites of disease will follow RECIST v.1.1 ([Appendix D](#)): CT (or MRI if allergic to contrast). The same radiographic procedure used to define measurable lesions must be used throughout the study for each patient. Assessment should be obtained regardless of cycle number and regardless of any dose withholds until tumor progression. Patients with clinical progression must obtain an unscheduled scan to document disease status per RECIST v1.1. Patients with suspected radiographic pseudoprogression, in the absence of clinical deterioration should remain on trial treatments and be rescanned at 4 weeks or later. If progression is confirmed on follow-up scan, then discontinue study treatments and follow study procedures for end-of-treatment and follow-ups. At the time of disease progression, patients randomized to trial Arm 2 may cross over to Arm 1 to receive AM0010 and nivolumab.

All randomized patients will be followed for OS every 8 weeks ( $\pm 7$  days) during the first year from the 90-day follow-up visit, every 12 weeks ( $\pm 7$  days) during the second year, and every 16 weeks ( $\pm 7$  days) thereafter. The survival follow-up will be conducted until death or study completion, whichever is first, whether or not trial drug was administered. For patients

who were randomized, but withdraw consent, survival (date of death) will be obtained by use of publicly available information.

Safety assessment will follow the guidelines provided in NCI-CTCAE v4.03 ([Appendix F](#)).

## 7.2 Overview

The trial consists of the following procedures:

(1) **Screening:** The screening period must occur within 21 days prior to dosing, unless otherwise stated. The screening visit may be counted as baseline (Day 1) if completed within 72 hours prior to dosing.

(2) **Treatment:** Patient will be randomized to either:

- Trial Arm 1: AM0010 self-administered as a SQ injection QD ( $\leq 80$  kg body weight = 0.8 mg or  $> 80$  kg body weight = 1.6 mg). Nivolumab will be administered at a fixed dose of 240 mg over approximately 30 minutes as an IV infusion on Day 1 of a 14-day cycle or at a fixed dose of 480 mg over approximately 30 minutes IV infusion on Day 1 of a 28-day cycle.

**OR**

- Trial Arm 2: Nivolumab will be administered at a fixed dose of 240 mg over approximately 30 minutes as an IV infusion on Day 1 of a 14-day cycle or at a fixed dose of 480 mg over approximately 30 minutes IV infusion on Day 1 of a 28-day cycle.

(3) **Clinical and Laboratory Assessments:**

Complete history, physical examination (Site/Organ System Status [includes: General appearance, skin, H/E/E/N/T – Thyroid, Pulmonary, Cardiovascular, Gastrointestinal, Musculoskeletal/ Extremities, Genitourinary/Breast, Lymph Nodes, Neurological, and Psychiatric]), ECOG performance status, height (screening visit only), weight, vital signs, and documentation of concomitant medications.

Laboratory studies: see Section [7.11](#).

(4) **Continued Treatment:**

At the time of disease progression, as judged by the Investigator, patients randomized to trial Arm 2 may cross over to Arm 1 and receive AM0010 and nivolumab.

(5) **End-of-Treatment:** Patients will return to the trial site 28 days ( $\pm 7$  days) after the last dose of trial drug for end-of-treatment assessments.

(6) **Follow-Up Period:**

During the extended safety observation period, all randomized patients will be followed for safety 60 and 90 days ( $\pm 7$  days) after the last dose of study treatment and monitored according to the SOA ([Appendix A](#)).

During the long-term follow-up period, all randomized patients who discontinue trial treatment before disease progression (per Investigator assessment) or patients randomized,

but not treated, will be followed for OS every 8 weeks ( $\pm 7$  days) during the first year from the 90-day follow-up visit, every 12 weeks ( $\pm 7$  days) during the second year, and every 16 weeks ( $\pm 7$  days) thereafter. The survival follow-up will be conducted until death or study completion, whichever is first.

The Investigator (or designee) will acquire the following information from patients who were randomized:

- Tumor assessment for all randomized patients who discontinue the trial treatment before disease progression or patients randomized but not treated. Tumor assessment will be repeated every 8 weeks ( $\pm 7$  days) during the study treatment and during the first year from discontinuation of the study treatment, every 12 weeks ( $\pm 7$  days) during the second year, and every 16 weeks ( $\pm 7$  days) thereafter, until study completion, disease progression, death, or receipt of new anti-cancer therapy, whichever is first.
- Subsequent cancer treatments (all randomized patients)
- Any SAEs considered to be related to trial treatment >90 days post last day of trial treatment, follow until resolution
- Date and cause of death (all randomized patients) (see [Appendix A](#)).

Scans will include CAPs and head, and will be sent to the central imaging vendor for archiving and possible assessment at a later date. If clinical progression is suspected, all relevant clinical documentation is to be submitted to the central imaging vendor for archiving.

### **7.3 Screening**

Informed consent must be obtained before any trial specific tests or evaluations are conducted.

The screening visit will occur within 21 days (unless otherwise stated) before administration of trial treatment and may be combined with baseline laboratory evaluations if both are done within 72 hours of initial dosing. Baseline scans for tumor assessment must be performed within 30 days of randomization. Trial eligibility will be based on fulfilling trial inclusion and exclusion criteria. The Investigator will use clinical judgment when determining the clinical significance of laboratory values at baseline and throughout the trial.

At the screening visit, information will be collected, and patients will have clinical evaluations as follows:

- Informed consent
- Demographics
- Medical and cancer history
- Physical examination (including Site/Organ System Status [includes: General appearance, skin, H/E/E/N/T – Thyroid, Pulmonary, Cardiovascular, Gastrointestinal, Musculoskeletal/Extremities, Genitourinary/Breast, Lymph Nodes, Neurological, and Psychiatric]), including height and weight

- Vital signs (5-minute sitting blood pressure, pulse, respiratory rate, oxygen saturation, and oral temperature)
- ECOG performance status assessment
- aPTT and International Normalized Ratio (INR) or PT
- Clinical laboratory tests (hematology, chemistry panel thyroid function (TSH, T3, and T4), and urinalysis)
- 12-lead ECG
- Pregnancy test (urine or serum) in WOCBP
- Radiologic tumor assessment including head and CAPs (within 30 days prior to randomization)
- PD-L1 expression as determined by any FDA-approved PD-L1 assay
- Concomitant medications
- Obtain pathology report of archival tissue.

If screening evaluations are not done within 72 hours of the initial dose of trial drug, the following evaluations will be repeated at a baseline visit:

- Physical examination (Site/Organ System Status [includes: General appearance, skin, H/E/E/N/T – Thyroid, Pulmonary, Cardiovascular, Gastrointestinal, Musculoskeletal/Extremities, Genitourinary/Breast, Lymph Nodes, Neurological, and Psychiatric]), including weight
- Vital signs (5-minute sitting blood pressure, pulse, respiratory rate, oxygen saturation, and oral temperature)
- ECOG performance status assessment
- Clinical laboratory tests (hematology, chemistry panel, coagulation tests, and urinalysis)
- Non-radiologic tumor assessment (if applicable).

## **7.4 Clinical Visits**

### **7.4.1 Clinic Evaluations**

Once a patient is enrolled, a mandatory tumor tissue sample for biomarker research should be submitted (preferably from the same block used for PD-L1 testing).

Physical examination, vital signs, 12-lead ECG, ECOG performance status assessment, thyroid function, and urinalysis will be assessed at Cycles 1, 3, 5, etc. Clinical laboratory tests (hematology, chemistry panel, and coagulation tests), concomitant medications, and AEs will be assessed at every cycle.

- Physical examination (Site/Organ System Status [includes: General appearance, skin, H/E/E/N/T – Thyroid, Pulmonary, Cardiovascular, Gastrointestinal, Musculoskeletal/Extremities, Genitourinary/Breast, Lymph Nodes, Neurological, and Psychiatric]) including weight.
- Vital signs (5-minute sitting blood pressure, pulse, respiratory rate, oxygen saturation, and oral temperature)
- 12-lead electrocardiogram (ECG)

- ECOG performance status assessment
- Clinical laboratory tests (hematology, chemistry panel, coagulation tests, thyroid function, and urinalysis)
- Biomarker blood sample
- Concomitant medications
- AEs

Note: The physical examination, weight measurement, and clinical laboratory tests may be performed up to 24 hours before dosing. Complete blood count (CBC) results must be available prior to infusion for every dose. If chemistry results are abnormal, assess again before dosing.

### **7.5 Tumor Assessments**

- CT or MRI (if allergic to contrast media) scans will be performed every 8 weeks ( $\pm 7$  days) during the study treatment and during the first year from discontinuation of the study treatment, every 12 weeks ( $\pm 7$  days) during the second year, and every 16 weeks ( $\pm 7$  days) thereafter, to evaluate response to treatment by RECIST v.1.1.
- The same radiographic procedure (includes head and CAPs) to define measurable lesions must be used throughout the trial for each patient.
- Patients will continue the assigned trial treatments until tumor progression (by RECIST v.1.1 criteria) by CT or MRI (if allergic to contrast media), withdrawal from the trial, or intolerance of therapy not manageable with dose modifications outlined in the protocol/package insert and/or supportive care. Note: patients with suspected radiographic pseudoprogression, in the absence of clinical deterioration, should remain on trial treatments and be rescanned at 4 weeks or later. If progression is confirmed on follow-up scan, study treatments will be discontinued or patients on Arm 2 may be eligible for crossover. Refer to Section 7.6.
- Patients who discontinue trial treatments with response of CR, PR, or SD will undergo CT or MRI scan evaluations per protocol until time of PD, death, study completion, or initiation of subsequent anti-cancer therapy, whichever is first.
- Patients who demonstrate clinical progression before their scans are due will have an unscheduled scan conducted to document disease status by RECIST v.1.1.
- The first scheduled tumor response assessment will be performed at 8 weeks ( $\pm 7$  days), and responders (CR or PR per RECIST v1.1) will have a confirmatory scan at  $\geq 4$  weeks after response has been established using the same technique as baseline scans.
- All CT/MRI scans for all patients randomized on the trial will be collected prospectively and submitted to a central imaging vendor for archiving. These scans may be independently reviewed at a later time at the request of Lilly.

### **7.6 Pseudoprogression and Confirmation of Disease Progression**

Accumulating evidence indicates a minority of patients treated with immunotherapy may derive clinical benefit despite initial evidence of PD.

Patients will be permitted to continue treatment beyond initial RECIST 1.1 defined PD if they meet the following criteria:

- Investigator-assessed clinical benefit, and do not have rapid disease progression
- Continue to meet all other study protocol eligibility criteria
- Tolerance of study drug
- Stable performance status

Treatment beyond progression will not delay an imminent intervention to prevent serious complications of disease progression (eg, CNS metastases).

A radiographic assessment/scan should be performed 4 weeks ( $\pm 7$  days) after original PD to determine whether there has been a decrease in tumor size, or continued PD. The assessment of clinical benefit should be balanced by clinical judgment as to whether the patients is clinically deteriorating and unlikely to receive any benefit from continued treatment with AM0010 and/or nivolumab. A confirmatory scan will be required in the case of clinical deterioration suspected to be disease progression.

For patients who continue AM0010 and/or nivolumab beyond initial progression, further progression is defined as an additional 10% increase in tumor burden volume from the time of initial PD. This includes an increase in the sum of all target lesions and/or the development of new measurable lesions.

When assessing disease progression, the Investigator should use a new baseline tumor burden that includes new lesions that developed at the time of initial progression. New lesions are considered measurable at the time of initial progression if the longest diameter is at least 10 mm (except for pathological lymph nodes which must have a short axis of at least 15 mm). Any new lesion considered non-measurable at the time of initial progression may become measurable and therefore included in the tumor burden volume if the longest diameter increases to at least 10 mm (except for pathological lymph nodes which must have a short axis of at least 15 mm).

For patients in both treatment arms, global deterioration of health status (to ECOG Performance Status 2 for example) requiring discontinuation of study treatments without objective evidence of disease progression at that time should be reported as “symptomatic deterioration.” Every effort should be made to document objective progression (ie, radiographic confirmation) even after discontinuation from study treatments.

### **7.7 Trial Drug Administration**

AM0010 is provided as a sterile, single use prefilled syringe, with a clear solution formulated at a concentration of 4 mg/mL. A pharmacy guide will be provided, which contains details regarding packaging, labeling, storage, (re)ordering and administration of AM0010 as well as FDA-approved labeling of nivolumab.

A trial-defined AM0010 and nivolumab treatment will begin on trial day 1. Patients on Arm 1 will dose AM0010 prior to initiation of nivolumab. Patients on Arm 1 will dose AM0010 according to their weight:

≤80 kg body weight = 0.8 mg

>80 kg body weight = 1.6 mg.

AM0010 dose recalculations are only required if a patient's body weight changed from ≤80 kg to >80 kg or vice versa only if weight fluctuates by ≥10% from baseline. Change in body weight should be calculated based on change from baseline weight.

Patients will be trained to self-administer AM0010 and will self-administer the dose throughout the trial starting with the first dose. A patient's caregiver may also be trained to perform SQ injections. Both the patient's and caregiver's training must be recorded in the patient's medical records. The Investigator or a qualified designee must be present during administration of the first dose. An AM0010 administration diary must be kept for dosing compliance monitoring.

Nivolumab will be administered according to 1 of 2 dosing schedules determined by the Investigator.

- Patients on ARM 1 (including crossover patients) will be administered nivolumab at a fixed dose of 240 mg over approximately 30 minutes IV infusion Q2W on Day 1 of each 14-day cycle or at a fixed-dose of 480 mg over approximately 30 minutes IV infusion on Day 1 Q4W of a 28-day cycle.
- Patients on ARM 2 will be administered nivolumab at a fixed dose of 240 mg over approximately 30 minutes IV infusion Q2W on Day 1 of each 14-day cycle or at a fixed-dose of 480 mg over approximately 30 minutes IV infusion on Day 1 Q4W of a 28-day cycle.

Nivolumab should be obtained by each site as per routine institutional practice. For preparation and complete prescribing information, refer to the most current prescribing information in the region. Investigators or designees will review the patient's hematology and chemistry panels, liver function tests, and the incidence of hematologic and non-hematologic toxicities prior to and during immunotherapy regimens.

Medications used to treat nivolumab-related infusion reactions (eg, diphenhydramine, acetaminophen/paracetamol, corticosteroids) considered NIMPs and will not be provided by the sponsor. These will be obtained by the investigational sites as marketed product, which should be stored in accordance to the package insert.

## **7.8 Continued Treatment**

### **7.8.1 Crossover**

At the time of disease progression (as assessed by the Investigator) patients randomized to trial Arm 2 may crossover to study Arm 1 to receive AM0010 and nivolumab. When progressive disease is noted on the scan for an ARM 2 patient, no more than 21 days should pass before the patient crosses over to ARM 1. The scans and/or clinical assessment at crossover will be used as a new baseline to determine response or PD on ARM 1.

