### **10.2 Trial Endpoints**

#### **10.2.1 Primary Endpoint**

- **Objective Response Rate**

The ORR is defined as the proportion of patients with a confirmed CR or PR relative to the efficacy population. The ORR is determined by the best response designation per RECIST v1.1 recorded between the date of randomization and the date of objectively documented progression or the date of subsequent anti-cancer therapy, or death, whichever occurs first. For patient without documented progression or subsequent anti-cancer therapy, all available response designations will contribute to the ORR determination. Confirmed responses are those that persist on repeat imaging scan  $\geq 4$  weeks after initial documentation of response. For patients who continue treatment beyond progression due to suspected pseudoprogression as outlined in Section 7.6. The objective response should be determined based on response assessment recorded at the CT scan done no less than 4 weeks after suspected pseudoprogression. If the patient subsequently responds or returns to baseline, that assessment of objective tumor response is achieved after pseudoprogression as the true response per RECIST v.1.1.

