| Arm 1 AM0010
Arm 1 & Arm 2 nivolumab   |                                 | QD (Not cycle dependent for either schedule of nivolumab)
Administered Q2W or Q4W; Each cycle = 4 weeks   |        |         |        |                      |        |                                |                                       |   |
| TUMOR AND SURVIVAL ASSESSMENTS   |                                 |  |        |         |        |                      |        |                                |                                       |   |
| Tumor assessment b   | Within 30 days of Randomization | Every 8 weeks (±7 days) during study treatment and during the first year from discontinuation of the study treatment every 12 weeks (±7 days) during the second year every 16 weeks (±7 days) thereafter |        |         |        |                      |        |                                |                                       |   |
| Survival a and treatment status  |                                 |  |        |         |        |                      |        |                                |                                       | X                                       |

Abbreviations: ADA = anti-drug antibody; aPTT = activated partial thromboplastin; ECG = electrocardiogram; Ht = height; INR = International Normalized Ratio; PD-L1 = programmed death ligand-1; PK = pharmacokinetics; PT = Prothrombin time; Q2W = every 2 weeks; Q4W = every 4 weeks; QD = everyday; TSH = thyroid stimulating hormone; Wt = weight.

- a All randomized patients will be followed for survival every 8 weeks (±7 days) during the first year from the 90-day follow-up visit, every 12 weeks (±7 days) during the second year, and every 16 weeks (±7 days) thereafter. The survival follow-up will be conducted until death or the study completion, whichever is first, whether or not trial drug was administered.
- b Tumor assessment will be performed for all randomized patients. Tumor assessment will be repeated until disease progression, death, or receipt of new anti-cancer therapy, or until study completion, whichever is first, whether or not study treatment was administered. When progressive disease is noted on the scan for an Arm 2 patient, no more than 21 days should pass before the patient can be considered for crossover to Arm 1.

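### The 21-day limit on Arm 2 crossover does not say which progression scan starts it; counted from the first scan, it conflicts with the 4-week rescan for suspected pseudoprogression

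*Protocol*

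**What the plan says.** **Crossover limit.** Protocol Section 7.8.1 starts from progression noted on the scan of an Arm 2 patient and says "no more than 21 days should pass before the patient crosses over to ARM 1". Appendix A footnote b gives the same number of days with a weaker verb: "no more than 21 days should pass before the patient can be considered for crossover to Arm 1". Crossover itself is optional: "patients randomized to trial Arm 2 may crossover to study Arm 1 to receive AM0010 and nivolumab".

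**Rescan for suspected pseudoprogression.** Under Section 7.1 these patients, "in the absence of clinical deterioration should remain on trial treatments and be rescanned at 4 weeks or later". The Synopsis, Section 3.0 and Section 7.5 use the same timing. Section 7.6 instead sets the scan at 4 weeks ±7 days, "after original PD to determine whether there has been a decrease in tumor size, or continued PD", and Appendix D uses that window too. A further Synopsis bullet says at least 4 weeks, again with ±7 days.

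**Order of confirmation and crossover.** The Synopsis (Trial Procedures) and Section 7.5 put the confirmatory scan before Arm 2 crossover. The Synopsis (Trial Design) and Sections 3.0, 7.2 and 7.8.1 also allow crossover at investigator-assessed progression, without mentioning confirmation.

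**Counting the response.** Protocol Section 10.2.1 says: "The objective response should be determined based on response assessment recorded at the CT scan done no less than 4 weeks after suspected pseudoprogression". A response seen afterwards is credited: "that assessment of objective tumor response is achieved after pseudoprogression as the true response per RECIST v.1.1". SAP Section 6.5.2.1 ends the primary ORR window at objectively documented progression or subsequent anti-cancer therapy. Its sentence on pseudoprogression is incomplete and only points to protocol Section 7.6, which has no rule for counting responses. SAP Section 6.5.2.2 places responses beyond pseudoprogression in ORR4. PFS sensitivity analysis 2 (SAP Section 6.5.5.1) does not count unconfirmed pseudoprogression as an event.

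**The concern.** Only Arm 2 has a crossover option that competes with waiting for a rescan. If the 21 days run from the first progression scan, an Arm 2 patient who wants crossover has to take it before the 4-week rescan is due. An Arm 1 patient with the same scan stays on treatment and is rescanned.

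Under protocol Section 10.2.1 a response seen at that rescan counts in the primary ORR. The trial is open-label, response is determined by the investigator, and each arm has about 25 patients, so a rule that works differently by arm can show in the result. The protocol and SAP also disagree on whether such a response belongs in the primary ORR at all, so the effect depends on which document the analyst follows.

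**Working it through.** The plan states no figure to reproduce here. The check compares day windows, with day 0 the first scan showing progression.

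**1. Clock started at the first scan.** The crossover window is days 0 to 21 (Section 7.8.1).

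| Rule | Days allowed | Days shared with 0–21 |
|---|---|---|
| Rescan at 4 weeks or later (Synopsis, Sections 3.0, 7.1, 7.5) | 4 × 7 = 28 onward | none; gap 28 − 21 = 7 days |
| Rescan at 4 weeks ±7 days (Section 7.6, Appendix D) | 28 − 7 = 21 to 28 + 7 = 35 | day 21 only |
| Rescan at ≥4 weeks (±7 days) (one Synopsis bullet) | 28 − 7 = 21 onward | day 21 only |
| CT for the ORR rule, no less than 4 weeks (Section 10.2.1) | 28 onward | none |

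The ±7-day window therefore makes a scan possible within the crossover limit, on one day, but a day-21 scan is too early for the ORR rule.

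**2. Clock started at the confirmatory scan.** Confirmation on day 21, 28 or 35 allows crossover through day 21 + 21 = 42, 28 + 21 = 49 or 35 + 21 = 56. There is no conflict.

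**3. Which scan is it?** Section 7.8.1 refers to progression noted on the scan. It mentions neither a confirmatory scan nor a pause for suspected pseudoprogression, so its plain reading is the first scan. No other section names the starting scan. The confirm-first order in the Synopsis and Section 7.5 makes the other reading a reasonable inference, but it remains an inference.

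**4. Can a scan after crossover repair this?** No. Section 7.8.1 resets the baseline at crossover, and SAP Section 6.7.4 uses the last assessment before crossover as the new baseline. Later scans describe the combination, not the progression on nivolumab alone.

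**5. Effect on ORR.** With 25 patients per arm, one responder is 1/25 = 4 percentage points. The documents give neither a pseudoprogression rate nor a crossover uptake, so the number of patients affected is unknown and may be zero.

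**6. Effect on PFS sensitivity analysis 2.** Neither that analysis nor SAP Table JZGD.6.1 says what to do with an Arm 2 patient who crosses over before a confirmatory scan. Read literally, the first progression is unconfirmed and not an event, which would flatter Arm 2. If it were counted as an event, Arm 2 would lose the allowance that a waiting Arm 1 patient gets. The direction is open.

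**The case against.** The strongest reply is that the sequence is already stated. The Synopsis applies the pseudoprogression provision to both arms, naming nivolumab alone, and the Synopsis and Section 7.5 put confirmation before Arm 2 crossover. Section 7.8.1 speaks of progression as assessed by the investigator, and an investigator who suspects pseudoprogression has arguably not yet made that assessment. On this view the 21 days run from confirmed progression and nothing conflicts. This is a tenable reading, but no section states it, and several allow crossover at progression without mentioning confirmation. Sites could follow either and believe themselves compliant.

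A second reply is that the SAP already protects the primary ORR by ending its window at documented progression and having a separate ORR4. That largely stands for the SAP taken alone. It does not remove the contrary rule in protocol Section 10.2.1, and the SAP's own pseudoprogression sentence is unfinished.

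Third, analyses are descriptive by arm and no formal comparison of ORR is planned. That is correct and lowers the stakes, but the two rates will still be read side by side.

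A reader might infer more: that Arm 2 patients must cross over, that the two time limits can never both be met, or that confirmation is in effect available only in Arm 1. The documents do not support these readings. Crossover is permissive throughout, an Arm 2 patient can stay on nivolumab and be rescanned, day 21 satisfies both Section 7.6 and the crossover limit, and the provision covers both arms.

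**Conclusion.** The inconsistency is real but narrower than it may look. The protocol does not identify the scan that starts the 21 days, its crossover wording differs between Section 7.8.1 and Appendix A, and its rescan windows differ between sections. If the first scan starts the clock, an Arm 2 patient who crosses over within the limit cannot have the scan that Section 10.2.1 requires for a post-pseudoprogression response on assigned treatment. An Arm 1 patient can. This rests on the first-scan reading and on the patient choosing crossover; under the confirmatory-scan reading it disappears.

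The protocol and SAP also place such responses differently, in the primary ORR and in ORR4 respectively. That disagreement does not depend on how the clock is read.

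A reader might go on to infer a bias of a given size in favour of Arm 1 across all endpoints. The documents do not support that. The 4 points per responder is arithmetic, not an estimate of bias. For ORR under Section 10.2.1 the asymmetry, if it occurs, favours Arm 1; for PFS sensitivity analysis 2 the direction is uncertain.

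**What to change.** **Protocol.** Reconcile the Synopsis, Sections 3.0, 7.1, 7.5, 7.6, 7.8.1 and 10.2.1, Appendix A footnote b and Appendix D. State which scan starts the 21 days and whether confirmation precedes crossover when pseudoprogression is suspected. The timing is a clinical decision, and none is proposed here.

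**SAP.** Complete the unfinished sentence in Section 6.5.2.1 so that the primary ORR window closes at the first RECIST v1.1 progression in both arms, with post-progression responses counted only in ORR4. Align protocol Section 10.2.1 with it. In Section 6.5.5.1, state how PFS sensitivity analysis 2 treats Arm 2 patients who cross over before a confirmatory scan.

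**Cost.** A protocol clarification and a sentence or two in the SAP, with no added data collection. The downside is that the primary ORR may be slightly lower than under the current Section 10.2.1 rule, because responses after pseudoprogression move to ORR4.
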